Study Phases	(1) Screening : Participants in the Mood, Mother, and Infant study are invited to participate in the Mood, Mother, and Child follow-up study. Those who meet inclusion criteria are scheduled for a mother-only visit for the Inhaled Oxytocin and HPA Axis Reactivity sub study.
Screening	
Study Treatment	(2) Intervention : Non-pregnant women will be randomized to either 24 IU of nasal OT or placebo prior to the Trier Social Stress Test.
Follow-Up	(3) Follow-up : Effects of nasal OT will be measured during the study visit, which will last about 2 hours.
Efficacy Evaluations	This is not a treatment study; this is a translational study to test the effect of oxytocin on the HPA axis.
Pharmacokinetic Evaluations	NA
Safety Evaluations	Prior to and during a 90-minute period following intranasal OT or placebo, mothers will be monitored for vital signs (heart rate, blood pressure, ear temperature), vascular resistance and mood.
Statistical And Analytic Plan	We will use a general linear model to test the hypothesis that participants who are randomized to receive nasal oxytocin experience lower HPA reactivity, operationalized using CRT area under the curve (AUC) during the TSST, to evaluate this proposed causal pathway
Data And Safety Monitoring Plan	Study PI, [name], will provide medical oversight for the randomized trial of oxytocin vs. placebo. Any adverse events, as well as any significant deterioration in mood, health or wellbeing, will be reported directly to [name] (the PI). All moderate and severe adverse events will be reported within one week to the FDA, whether anticipated or unanticipated.

3. Background and Rationale

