5.2. Intervention/Treatment procedure for study visit

Non-pregnant women will be randomized to either 24 IU of nasal oxytocin (OT) or placebo. The Investigational Drug Service (IDS) will use a random number generator to prepare a randomization table. Participants will be block randomized by risk status at enrollment in the Mood, Mother and Infant (MMI) study, as verified by structured clinical diagnostic interview (No history of depression or anxiety, Past depression or anxiety, current depression or anxiety). Both participants and study personnel will be blinded to allocation group. At the end of the protocol, participants will be asked which condition they believed they were in ('oxytocin,' 'control,' 'not sure') to ascertain success of blinding. Forty minutes after treatment, women will undergo the Trier Social Stress Test (TSST), comprised of a speech task and a math task; the TSST reliably induces large and consistent HPA and cardiovascular responses^{16,17}. The TSST is administered as follows: Pre-Task Instructions: (5 minutes) Subjects will be introduced to 3 people (the 'selection committee') and asked to assume the role of a job applicant. Anticipation Period: The subject prepares her speech for 3 minutes in the presence of the committee. Speech: The committee asks the subject to deliver her talk for 5 minutes while being video and audio-recorded. If the subject finishes early, the committee

responds with prepared questions to ensure that she speaks for the entire 5 minutes. These questions are designed to be non-harassing but to create a feeling of lack of predictability/controllability (e.g., "Do you have any enemies?") Serial Subtraction (PASST): The committee will ask the subject to subtract the number 7 from 2000 as quickly and accurately as possible for 5 minutes. For each mistake, the committee says "Stop -- mistake -- start over at 2000." Stress Recovery: The subject sits quietly alone for 20 minutes.

- 5.3. Follow- up procedures : NA**
- 5.4. Unscheduled visits: NA**
- 5.5. Concomitant Medication documentation: NA**
- 5.6. Rescue medication administration (if applicable): NA**
- 5.7. Subject Completion/ Withdrawal procedures**

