All participants will also be reminded before starting the procedures that they would be free to withdraw at any time without penalty, and may contact our IRB review board or the Principal Investigator (numbers are provided) if she feels that rights regarding privacy or risk to health have been infringed. The right of the participants to withdraw from the study or to refuse any procedure will be made absolutely clear. The original consent form will be kept in a secured location in a locked office, and a copy will be provided to the participant.

- 5.8. Screen failure procedures**

Some mothers who are eligible for Inhaled Oxytocin and HPA Axis Reactivity are expected to be pregnant at the time of the follow-up study. Because oxytocin can cause contractions, the Inhaled Oxytocin and HPA Axis Reactivity visit will not be scheduled while the mother is known to be pregnant, and will be deferred until 6 months postpartum. All mothers without a known pregnancy will be screened with a urine pregnancy test on arrival to the Mother Visit; if the pregnancy test is positive, the nasal OT and TSST protocol will not be performed.

- 5.9. STUDY EVALUATIONS AND MEASUREMENTS**

Mobile Impedance Cardiographs (MindWare Tech Ltd, Gahanna, OH) will be used to measure cardiac rate, interbeat interval and pre-ejection period (PEP) in mothers and children. MindWare HRV software will be used to derive respiration and to calculate high frequency HRV and respiratory sinus arrhythmia from the IBI series as indices of parasympathetic activity. Respiratory rate will be used in all HRV analyses. MindWare Impedance Cardiography Analysis software will calculate cardiac time intervals (PEP, LVET), stroke volume and cardiac output. PEP will index sympathetic activation.

Blood will be collected at baseline, during the speech and math tasks, and at 10 and 20 minutes of recovery, as HPA-axis responses are reliably found 10-30 minutes following the TSST. Evidence regarding optimal timing of stress testing is conflicting. Visits will be scheduled for 1 pm to increase likelihood of detecting a stress response unopposed by the circadian influence, based on the experience of investigators in our laboratory and published studies of postpartum women. These investigators have found menstrual

cycle phase does not affect TSST results; therefore visits will not be scheduled based on cycle phase.

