5.14. Statistical Methods

Our primary objective is to test the extent to which nasal oxytocin compared with placebo alters the trajectory of CRT during the TSST. We will use repeated measures analysis to quantify the effects of group (OT vs. placebo) on CRT trajectory during the TSST. We will first establish the shape of unconditional trajectory models for CRT using generalized linear mixed models with a random intercept and slopes to account for individual differences in CRT trajectories. We will test the fit of quadratic, cubic, and exponential effects of time as well as linear spline models. The most parsimonious unconditional trajectory model that fits the data well will be used for hypothesis testing. The intercept of the CRT trajectories will be placed at peak CRT. We will regress growth parameters (intercept and slopes) on treatment arm. A significant effect of treatment arm on the intercept will indicate a difference in peak CRT across groups, and a

significant effect of treatment arm on slopes will indicate differences in the rate of recovery during the TSST.

For secondary endpoints, we will similarly use repeated measures analysis to quantify the effects of group (OT vs. placebo), time, and group x time on each measure's trajectory during the TSST. We will use repeated measures analysis with an interaction term to test the extent to which maternal depression/anxiety and OXTR genotype modifies the effect of oxytocin vs. placebo on measures of stress reactivity.

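### Section 5.14 reads an arm effect on unrestricted slopes as recovery, so an effect on the cortisol rise alone can be reported as a change in recovery

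*Combined protocol and SAP*

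**What the plan says.** The primary endpoint is the cortisol trajectory during the stress test (5.13.1). Section 5.14 chooses its shape from the data: "We will test the fit of quadratic, cubic, and exponential effects of time as well as linear spline models". Then: "The most parsimonious unconditional trajectory model that fits the data well will be used for hypothesis testing". The origin is fixed: "The intercept of the CRT trajectories will be placed at peak CRT". The intercept and all slopes are regressed on arm and given meanings. For the intercept: "A significant effect of treatment arm on the intercept will indicate a difference in peak CRT across groups". For the rest, a "significant effect of treatment arm on slopes will indicate differences in the rate of recovery during the TSST".

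Section 5.14 does not say which slope is meant, gives no reading for a difference in the rise, and does not say whether peak time is common to all women or individual.

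The sampling covers both sides of the peak. Section 5.9 states: "Blood will be collected at baseline, during the speech and math tasks, and at 10 and 20 minutes of recovery". Section 5.2 gives the length of recovery: "Stress Recovery: The subject sits quietly alone for 20 minutes".

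The synopsis states the hypothesis on another summary, that "participants who are randomized to receive nasal oxytocin experience lower HPA reactivity, operationalized using CRT area under the curve (AUC) during the TSST".

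**The concern.** The recovery reading is right only for a coefficient that describes the decline after the peak. In a linear spline, the slope before the peak is the rise. In a quadratic or cubic with its origin at the peak, the linear term is the tangent at that point and the higher terms bend rise and fall together.

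Suppose oxytocin only blunts the rise: arms equal at baseline, d apart at the peak, parallel afterwards. The intercept should show the lower peak. A slope term can also differ by arm, and 5.14 would then have the report say that recovery differs, which is untrue in that case. Reactivity and recovery are different biological conclusions, and this concerns the primary endpoint. The AUC in the synopsis cannot settle it, because AUC falls with a smaller rise or with a faster recovery.

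**Working it through.** **1. Reproduce the plan's figure.** Section 5.15 reduces power to a two-sample t-test on each woman's growth parameter. With 75 per arm and d = 0.46, the noncentrality is 0.46 × √(75/2) = 2.82 on 148 df. The two-sided 5% critical value is 1.976 and power is 79.9%, which matches the 80% behind the 5.15 table.

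**2. Draw times.** From 5.2, in minutes after drug: test starts at 40; instructions 5, preparation 3, speech 5 (48–53), arithmetic 5 (53–58). Taking mid-task draws (an assumption), the five draws in 5.9 fall at 0, 50.5, 55.5, 68 and 78. An eight-draw set, to match the count in 5.15, was assumed at 0, 20, 40, 50.5, 55.5, 68, 78 and 88.

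**3. The mechanism in one case.** Take the five draws, peak at 68, a rise-only effect starting at 40, and correlation 0.7 between draws.
- Arm gap: 0 at baseline; (50.5 − 40)/28 = 0.375d; (55.5 − 40)/28 = 0.554d; then d and d. The true post-peak difference in change is d − d = 0.
- Least-squares quadratic in (t − 68): the gap's linear coefficient is 0.02446d per minute, not 0. Its between-woman SD is 0.02835.
- Noncentrality: 0.02446 × 0.46 / 0.02835 × √37.5 = 2.43, so the linear term alone is significant in about 67% of trials.

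This is the least favourable of the twelve five-draw quadratic scenarios. It shows the route, not the typical size.

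**4. Across assumptions.** There were 24 scenarios: five or eight draws; peak at 55.5 or 68; gap opening linearly from baseline or from minute 40; correlation 0.5, 0.7 or 0.95·exp(−lag/98). SD was 1 at every draw, with 75 per arm, d = 0.46, two-sided 0.05 and t-tests on per-woman coefficients. Recovery is identical in both arms. Repeat runs differ by a point or two.

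| Imposed shape | Lower peak found | Some slope significant | Both | Slope only (median) |
|---|---|---|---|---|
| Quadratic | 50–92% | 15–100% | 14–78% | 1–44% (9%) |
| Cubic | 62–91% | 8–99% | 6–77% | 1–36% (6%) |
| Spline knotted at peak | 53–92% | 73–100% | 48–88% | 6–38% (14%) |

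On the five listed draws, the median for both together is about 30% (quadratic) and 14% (cubic). With no drug effect, some slope is significant in 6–9% (quadratic), 7–12% (cubic) and 8–10% (spline), so the lowest cubic rates are no more than background. At d = 0.73, slope-only has medians below 1% and a maximum of 12%.

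**5. Quantities that do isolate recovery.** The arm difference in change from the peak-time draw to the last draw, with time as a category, rejects in about 4–6% throughout. So does the post-peak slope of a spline with knots at test start and at peak. With a knot only at the peak, the post-peak slope rejects in about 5% if the rise is linear from baseline, but in about 7–34% if it starts at minute 40.

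**6. The scale of recovery.** If the rises are R and R − d and both lose a fraction f by the last draw, the absolute declines are fR and f(R − d). They differ by f·d. For f from 0.25 to 0.75 (assumed) and d = 0.46, that is 0.115 to 0.345 SD, although proportional recovery is equal.

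**The case against.** The best defence is that 5.14 pairs peak (intercept) with recovery (slopes), so its authors may have meant only the slope leaving the peak. With suitably placed knots that reading has about 5% error. But the text does not say so, and it does not help if a quadratic or cubic is chosen, where no single coefficient is the recovery rate.

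The size is also fairly contested, and several points stand. The high spline figures are mostly the pre-peak slope detecting a rise difference that is really there; a reader might take 73–100% as a false-positive rate, and it is not. The higher polynomial rates come mainly from eight draws at assumed times. Parallel arms after the peak are assumed too: 5.15 quotes differences of 1.03, 1.22 and 0.73 SD from an earlier study without their timing. If those are in time order, the gap narrows and absolute recovery does differ. Whether a recovery statement is false therefore depends on how recovery is defined.

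A reader might also infer that the primary test is invalid, or that a true lower peak would be missed and replaced by a recovery claim. The documents do not support either. The arm tests still address whether the trajectory differs, the intercept is read correctly, and at the plan's detectable difference a slope result without an intercept result is the less common outcome. The five draws in 5.9 against eight assessments in 5.15 is a separate matter, which the appendix schematic (not shown) may resolve.

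**Conclusion.** The slope sentence is wrong as written and should be replaced. The text supports this firmly: the slopes are unrestricted, pre-peak draws are in the trajectory, and no other section narrows the rule.

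The size is illustrative. At 0.46 SD a rise-only effect yields a correct lower peak with a false recovery statement in roughly 14–78% (quadratic) or 6–77% (cubic) of simulated trials, nearer 30% and 14% on the listed draws. These rates rest on assumed times, correlations and shapes. Exponential models were not simulated, and no rate is given for the shape-selection step because it would depend on the curve assumed.

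That the lower peak is usually found holds at about 0.46 SD and above. Under a separate set of assumed variances it was found in only 17–23% of trials at 0.2 SD and 34–45% at 0.3 SD, while some slope was significant in 32–39% and 60–67%.

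**What to change.** In 5.14 keep the intercept sentence and replace the slope sentence with these rules:

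1. An arm effect on a pre-peak slope is reported as reactivity.
2. Only a prespecified post-peak quantity is reported as recovery. Preferred: the arm difference in cortisol change from the peak-time draw to the last recovery draw, with time as a category. Alternative: the post-peak slope of a spline with knots at test start and at peak.
3. Raw quadratic or cubic coefficients are not read as recovery. An exponential rate is, only if it describes the post-peak decline alone.
4. State whether recovery is absolute or relative to the rise. If absolute, report it beside the peak difference.
5. State how peak time is set, from data pooled over arms before unblinding, and report any arm difference in peak timing.

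The cost is a few sentences, with no new data and no change in sample size. There are three downsides:
- Power for recovery is lower if few draws follow the peak: for an assumed difference of 0.46 SD per 20 minutes, 29–75% with one later draw at 10 minutes, against 80–99% with a last draw at 20 minutes.
- The contrast does not separate slower recovery from a later peak. An assumed 4-minute delay, with a rise of 1 SD over 28 minutes and a fall of 0.5 SD over 20, shifts it by (1/28 + 0.5/20) × 4 = 0.243 SD, and it then rejects in 32–79%.
- With only the five listed draws, none falls at test start, and the two-knot stressor-to-peak slope has only about 15–78% power at 0.46 SD. In that case the intercept at peak should carry the reactivity conclusion.

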3.5.2. Secondary Objective

The secondary objective of this experiment is to test the extent to which oxytocin compared with placebo alters other measures of stress reactivity during the Trier Social Stress Test. We will measure trajectory of ACTH, lagged association between ACTH and CRT, heart rate variability, and pre-ejection period during the Trier Social Stress Test.

3.5.3. Other objectives:

We will test the extent to which maternal depression/anxiety modifies the effect of OT on CRT, ACTH, lagged association between ACTH and CRT, heart rate variability, and pre-ejection period during the Trier Social Stress Test.

We will test the extent to which OXRT genotype modifies the effect of OT on CRT, ACTH, lagged association between ACTH and CRT, heart rate variability, and pre-ejection period during the Trier Social Stress Test.

4. Investigational Plan

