5.13.2. Secondary Endpoint

Our secondary end points comprise other measures of stress reactivity during the TSST, including trajectory of ACTH, lagged association between ACTH and CRT, heart rate variability, and pre-ejection period.

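### The model set for secondary endpoints in section 5.14 has no coefficient for the lagged ACTH-cortisol association, so that endpoint is not estimated as written

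*Combined protocol and SAP*

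**What the plan says.** Section 5.13.2 lists the secondary endpoints as other measures of stress reactivity, "including trajectory of ACTH, lagged association between ACTH and CRT, heart rate variability, and pre-ejection period". The lagged association stands beside the ACTH trajectory as an item of its own. Section 3.5.2 and the synopsis carry the same list as the secondary objective. Section 3.5.3 makes it an outcome of the effect-modification objectives as well, asking whether "maternal depression/anxiety modifies the effect of OT on CRT, ACTH, lagged association between ACTH and CRT" and the remaining measures, and asks the same of OXTR genotype.

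The analysis text is in section 5.14. Its rule for secondary outcomes is stated once: "we will similarly use repeated measures analysis to quantify the effects of group (OT vs. placebo), time, and group x time on each" of the measures, taken as a trajectory over the stress test. The only further term is in the next sentence, "repeated measures analysis with an interaction term to test the extent to which maternal depression/anxiety and OXTR genotype modifies the effect" of oxytocin. No section puts ACTH in a model for cortisol, fits the two hormones jointly, defines the lag, or names the coefficient to be compared between arms.

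On sampling, section 5.9 says "Blood will be collected at baseline, during the speech and math tasks, and at 10 and 20 minutes of recovery", which names about five draws. Section 5.15 says cortisol is assessed 8 times. The number of ACTH samples is not stated.

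**The concern.** Group, time and group x time describe how the mean of one series moves in each arm. A lagged association is a relation between two series. Two arms can share the same mean ACTH curve and the same mean cortisol curve and still differ in how strongly a woman's cortisol follows her own earlier ACTH. So the stated rule does not fit one of the endpoints it is meant to cover.

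The trial has a reason to care. Section 3.4 cites a small study in which the expected ACTH-cortisol correlations were seen in euthymic women but not in women with depressive symptoms. It also cites a study in which recent breastfeeding lowered cortisol without lowering ACTH. If the model is not fixed in advance, someone must choose the lag, the draw pairs and the split between within-woman and between-woman association after the data are in hand. Each of those choices can change the answer.

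**Working it through.** **The plan's own figure.** The only power figures (section 5.15) are for cortisol growth parameters: 0.74 SD at 30 per group to 0.46 SD at 75, with 80% power and alpha 0.05 (two-sided assumed). The normal approximation (1.960 + 0.842) x sqrt(2/n) gives 0.723 at n = 30 and 0.458 at n = 75. The noncentral t gives 0.736 and 0.461. All ten tabulated values agree with the noncentral t within 0.005. The table is sound, but it says nothing about the lagged association.

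**What each model contains.**

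- Stated: E(Y at draw t) = a_t + d_t x arm, for one series Y at a time. The tests concern d_t.
- Needed: cortisol at t = a_t + d_t x arm + k x (woman's mean ACTH) + b x L + h x arm x L + woman effect + error, where L is her ACTH at the previous draw minus her own mean. The treatment effect on coupling is h.

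Neither b nor h can be read from d_t.

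**When a coupling change shows in mean cortisol.** If coupling also acts on the mean ACTH rise m, the cortisol difference between arms at the next draw is h x m. With assumed slopes 0.5 and 0.2, h = -0.3. A rise of 0 gives a difference of 0; a rise of 1 SD gives 0.3; a rise of 3 SD gives 0.9. Conversely, if coupling is the same in both arms but mean ACTH differs by D, mean cortisol differs by 0.5 x D. So a cortisol group x time result is neither necessary nor sufficient for a coupling change.

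**Simulation.** Assumptions: 75 per arm (150 / 2), slopes 0.5 vs 0.2, unit-scale noise, 5% tests.

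| Setting | Cortisol group x time rejects | Arm x lagged ACTH rejects |
|---|---|---|
| Equal mean curves, 5 draws | about 5% | 89% |
| Equal mean curves, 8 draws | about 5% | 99% |
| Mean ACTH rise 1 to 3 SD, 5 draws | about 13% to 86% | |
| Mean ACTH rise 1 to 3 SD, 8 draws | about 18% to 97% | |

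A second set of runs put the cortisol test at 19% to 99% (5 draws) and 21% to 99% (8 draws) over the same rises, so those two rows depend on the detail assumed.

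A separate simulation with slopes 0.6 vs 0.2 and equal mean curves (300 runs) agreed on the first two rows. Group x time rejected in 4.7% (ACTH) and 6.0% (cortisol) of runs with 8 draws, and in 5.7% and 6.0% with 5. The interaction was found in 100% and 99%. In a companion 300-run setting with equal slopes, the ACTH test rejected in 10%, so these rates are approximate.

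The power of the new term depends heavily on the assumptions. With autocorrelated ACTH (0.5) and slopes 0.5 vs 0.2 it was 76% (5 draws) and 97% (8). Halving the slope difference gave 24% and 52%.

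**Draw intervals.** Section 5.2 starts the stress test 40 minutes after dosing, with 5 minutes of instructions and 3 of preparation. The speech starts at 40 + 5 + 3 = 48 min, the math task at 53, and recovery at 58. The recovery draws fall at 68 and 78. If draws are taken at task start, the gaps after the speech draw are 53 - 48 = 5, 68 - 53 = 15 and 78 - 68 = 10 min. If the baseline draw is pre-dose, the first gap is 48 min or more. Section 5.9 lists baseline separately from 40 minutes after dosing for the questionnaire, which supports a pre-dose baseline but does not settle it for blood.

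Dropping the baseline pair therefore leaves gaps of 5, 15 and 10 min, still unequal. With 5 draws it also lowers power from about 89% to 72% under the assumed slopes.

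**The case against.** The fairest defence is that section 5.14 is a one-sentence summary for four measures. The investigators name the lagged association repeatedly and plainly mean to estimate it, and a repeated-measures model of cortisol can carry lagged ACTH as a time-varying covariate. All of that is true, and nothing in the plan forbids it. But the sentence lists the effects to be tested, and lagged ACTH is not among them. Stretching its wording to a derived coupling measure does not help, because no such measure is defined at each time point.

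A reader might infer three stronger things that the documents do not support.

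- *That the data cannot yield this endpoint.* They can; the gap is in the text.
- *That the planned tests would be blind to altered coupling.* That holds only when mean curves are equal. Section 5.2 describes the stressor as producing strong and dependable HPA responses, and the breastfeeding study in section 3.4 found a pattern visible in mean curves. With a mean ACTH rise, the cortisol test may well reject. It would still not say whether coupling changed.
- *That the protocol treats coupling as the defining sign of HPA dysregulation.* Section 3.4 cites one study of 13 and 9 women for it, among several lines of evidence.

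The timing argument is also conditional. Draws are taken during the tasks, not necessarily at their start, and the visit schematic in the appendix is not available here and may give the times. It could settle the intervals, but not the missing model term.

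**Conclusion.** The point stands as a mismatch between a named secondary endpoint and the only model given for it. It is confined to the lagged ACTH-cortisol association and to the two exploratory modifier analyses that use it. The primary endpoint, the sample size and the other three secondary endpoints are untouched.

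Confidence is high on the structure, which needs no simulation. The size is illustrative: group x time rejects at about 5% when mean curves are equal, and at anything from 13% to 99% across the runs with an assumed ACTH rise of 1 to 3 SD. The 89% and 99% for the direct test rest on assumed slopes and noise, and do not predict the trial's power. The plan should be changed, but the matter does not threaten the trial's main conclusion.

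**What to change.** Add to section 5.14, for this endpoint: a repeated-measures model of cortisol at each draw on time, arm, arm x time, each woman's mean ACTH, her within-woman deviation in ACTH at the previous draw, and arm x that deviation, with a woman-level random effect. Name the arm x lagged-deviation coefficient as the test. A bivariate model of the two hormones would be an acceptable alternative if its tested parameter is stated. For the modifier objectives, add the modifier's interaction with that coefficient and label it exploratory.

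Reconcile the five or so draws in section 5.9 with the 8 cortisol assessments in section 5.15, give the number of ACTH samples, and state before unblinding which draw pairs form the lag.

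Because the intervals are unequal, include interval length and its interaction with lagged ACTH. If time is entered draw by draw, the interval's main effect is absorbed and the interaction is what matters. Centre the interval at a stated value so that the lag coefficient has a clear meaning. Exclude a long baseline pair only as a sensitivity analysis, since exclusion costs power and does not equalise the remaining gaps.

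The cost is one paragraph of text and one more model, with no new data.
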